10.1.3. Time adjusted OCS Burden

Time adjusted AUC is a measure of steroid burden and approximates the mean steroid usage post-baseline for each patient. For each patient, it is calculated and summarized as follows,

$$Time\ Adjusted\ AUC = \sum_{t=M}^{N-1} \frac{AUC}{N-M} = \sum_{t=M}^{N-1} \frac{(C_t + C_{t'}) (t' - t)}{2(N-M)},$$

where

C_x is the OCS dose in mg on day x ,

t' is the study day of the next known OCS daily dose after day t ,

M and N are start and end study days of the analysis periods of interest. In this study, we are interested in the time periods a) Day 1 through end of dosing period (30 days after last dose) or day of last known OCS dose (if earlier than end of dosing period) and b) Day 51 through end of dosing period (30 days after last dose) or day of last known OCS dose (if earlier than end of dosing period).

Similarly, change from baseline and percent change from baseline at each diary entry will be used as C_x in the formula above, and analyses will be repeated.

aTyr Pharma, Inc.
Study ATYR1923-C-002 Statistical Analysis Plan
IND#: 133692

FINAL Version 1.0
2021-08-02

In addition, active treatment arm for each cohort and combined active arm are compared to combined placebo using the following pseudo code.

```
proc glm data = auc;  
  class treatment(ref=Placebo);  
  model auc = treatment baselineOCS / solution;  
  lsmeans treatment / pdiff=control("Placebo") adjust=T cl;  
run;
```

The difference between LS means, 95% Confidence Intervals and p-values will be presented.

Time adjusted AUC for Day 1/51 through end of treatment periods will be summarized using density and box plots by treatment.

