4. INVESTIGATIONAL PLAN

4.1. **Overall Study Design and Plan**

This randomized, double-blind, placebo-controlled, study will evaluate the safety, tolerability, immunogenicity, PK, and preliminary efficacy of multiple ascending doses of IV ATYR1923 in patients with pulmonary sarcoidosis undergoing a protocol-guided OCS tapering regimen.

This study will consist of 3 staggered multiple dose cohorts, as shown in Table 2.

	Dose		Dosing	
Cohort	(mg/kg)	# of Doses	Frequency	1

Planned Dose Cohorts

Cohort	Dose (mg/kg)	# of Doses	Dosing Frequency	N	Ratio ATYR1923: Placebo
1	1.0	6	Every 4 weeks	12	2:1
2	3.0	6	Every 4 weeks	12	2:1
3	5.0	6	Every 4 weeks	12	2:1

Each eligible patient will participate in only one cohort during the study. Within each cohort, 12 patients will be randomized 2:1 (block size of 6) to ATYR1923 (N=8) or placebo (N=4). Study drug will be administered via IV infusion every 4 weeks for a total of 6 doses (20 weeks of treatment). The follow-up study visit is scheduled for 4 weeks after the last infusion. The ATYR1923 doses levels to be evaluated are 1.0 mg/kg, 3.0 mg/kg, and 5.0 mg/kg. In total, approximately 36 patients with pulmonary sarcoidosis are planned to be randomized. The dose-escalation procedure is described in Section 7.1.3.1.

Day 1 is the calendar day of first infusion.

Starting on Day 15, patients will begin a taper (reduction) in OCS (per the ATYR1923-C-002 Oral Corticosteroid Taper Guidelines) from their starting dose of 10-25 mg/day of prednisone (or equivalent) to a target dose of 5 mg/day, to be completed on or before Day 50. The OCS dose will be tapered by 5.0 mg/day every 1 to 2 weeks, depending on the starting dose. Smaller incremental titrations to the target dose of 5 mg/day by Day 50 may be implemented per Investigator judgement. Patients will be maintained at the target dose of 5.0 mg/day (or equivalent) through Week 24/End-of-Study (EOS). Optionally, further titrations in the OCS dose to below 5 mg/day may be attempted after the Week 16 visit, if determined by the Investigator to be feasible.

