7.1.3. Method of Assigning Patients to Treatment Cohorts

After obtaining informed consent, patients will be screened according to the inclusion and exclusion criteria and will be assigned to a cohort based on their availability. Within each cohort, 12 patients will be randomized 2:1 (block size of 6) in a blinded fashion to ATYR1923 (N=8) or placebo (N=4).

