7.1.3.1. Dose Escalation Procedure

Cohorts 1 through 3 will be enrolled sequentially in a staggered manner. After at least 6 patients of a given cohort have received at least 3 infusions of study drug (ATYR1923 or placebo), cumulative unblinded safety data (including but not limited to any reported AEs, ECG recordings, clinical laboratory tests, and vital signs) will be reviewed by the DSMB. Enrollment in the next scheduled cohort may commence after this review is completed, dose escalation is approved, and the remaining 6 patients have been randomized in the previous cohort. Dose escalation will continue in this manner until the highest planned dose level of ATYR1923 is reached, or the criteria for pausing enrollment have been met (see Section 7.1.3.2).

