7.1.4.2. Current Study in Patients with Pulmonary Sarcoidosis

The proposed doses in the current study in patients with pulmonary sarcoidosis are 1.0 mg/kg (Cohort 1), 3.0 mg/kg (Cohort 2), and 5.0 mg/kg (Cohort 3). Cohorts will be enrolled sequentially in a staggered manner.

Selection of the proposed doses is primarily informed by clinical and pharmacological findings from ATYR1923-C-001, in which single doses of ATYR1923 were well tolerated across the broad dose range from 0.03 up to 5.0 mg/kg, with no clear dose-relationship with regard to the incidence of TEAEs, or changes in clinical laboratory parameters or other safety measures. No SAEs or severe AEs were reported at any dose, indicating that the starting dose of 1.0 mg/kg dose in this study should be acceptable.

Repeat administration of ATYR1923 once monthly is expected to result in little or no accumulation of peak (ie, maximum concentration [C_{max}]) and total (ie, area under the curve [AUC]) serum exposure measures at steady-state when compared to single dosing. For example, C_{max} and area under the curve from time zero to 168 hours (AUC[0-168h]) after the 6th monthly dose of ATYR1923 at 5 mg/kg is predicted to be 109,618 ng/mL and 3,577,275 ng·h/mL, respectively; estimates that are highly similar to the values observed after a single dose of ATYR1923 at 5 mg/kg in ATYR1923-C-001 (109,250 ng/mL and 3,417,001 ng·h/mL, respectively).

In a Good Laboratory Practice-compliant 6-month duration toxicology study in NHPs, the NOAEL was 60 mg/kg by IV injection once weekly, the highest dose administered. The mean serum exposures (AUC_[0-168h]) measured at the NOAEL in this study ranged from 27,900,000 ng·h/mL (Day 1) to 44,400,000 ng·h/mL (Day 176). Comparison of the mean serum exposures observed in NHPs with those predicted in subjects after the 6th monthly dose of ATYR1923 at the 5 mg/kg dose (3,577,275 ng·h/mL) estimates a safety margin of 8-12-fold. Safety margins based on comparison of mean maximal concentrations (mean C₀ ranged from 1,880,000-2,080,000 ng/mL in NHPs versus the mean predicted C_{max} of 109,618 ng/mL in humans) are higher at 17-19-fold. Therefore, repeat-dose administration of ATYR1923 to patients over a 6-month duration at doses up to 5 mg/kg is expected to produce mean serum exposures that remain well below those seen in animal toxicity testing for up to 6 months.

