5.3. Randomization and Blinding

It is planned that 36 patients with pulmonary sarcoidosis will be randomized into one of 3 sequential cohorts, each comprising 12 patients allocated 2:1 (block size of 6) to ATYR1923:Placebo.

The master randomization schedule will be made of randomly permuted blocks of appropriate sizes, as determined by the unblinded study team member producing the schedule. The schedule will be generated electronically.

For patients who are replaced, the replacements should take the same treatment assignment as the original patient to ensure that the treatment groups stay balanced.

The randomization code will be produced within the interactive web response system (IWRS). The study center pharmacist will be provided access to the randomization code within the IWRS and through notifications generated by the IWRS. The laboratory where the PK samples are to be analyzed will also be provided access to distinguish between samples of patients dosed with ATYR1923 versus placebo.

Patients who withdraw for any reason without completing all screening evaluations successfully, will be considered “screen failures”.

Randomization will be performed using an IWRS. The patient will be issued a randomization number only after the patient has met all Inclusion and Exclusion criteria.

The following controls will be employed to maintain the double-blind status of the study:

- The infusion solution containing active drug and placebo will be indistinguishable in appearance.
- The study center pharmacist will have access to randomized treatment assignments via IWRS for dispensing purposes; treatment assignments will be accessible only to the pharmacist and authorized personnel and will be maintained in a blinded fashion.

aTyr Pharma, Inc.
Study ATYR1923-C-002 Statistical Analysis Plan
IND#: 133692

FINAL Version 1.0
2021-08-02

Rules for unblinding a patient for safety reasons are fully described in the Protocol and not repeated herein this SAP.

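### Patients are randomised within three sequential dose cohorts, but no specified efficacy analysis includes cohort, and two thirds of each dose's placebo comparator comes from other cohorts

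*SAP*

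**What the plan says.** **Design.** Under Protocol 7.1.3.1, "Cohorts 1 through 3 will be enrolled sequentially in a staggered manner". The next cohort may open only after the safety review is completed, escalation is approved, "and the remaining 6 patients have been randomized in the previous cohort". Under Protocol 7.1.3, patients "will be assigned to a cohort based on their availability". Protocol 7.1.4.2 ties Cohorts 1, 2 and 3 to 1.0, 3.0 and 5.0 mg/kg. SAP 5.3 has patients "randomized into one of 3 sequential cohorts, each comprising 12 patients allocated 2:1 (block size of 6) to ATYR1923:Placebo", which is 8 active and 4 placebo per cohort.

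**Analysis.** In SAP 10.1.3 the "active treatment arm for each cohort and combined active arm are compared to combined placebo", using "model auc = treatment baselineOCS / solution". The other specified analyses also omit cohort:

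- SAP 10.1.5: Fisher's exact test (each dose v combined placebo), and log-rank and Wilcoxon tests (each dose and combined active v placebo), all unstratified.
- SAP 11.1.1.1, MMRM for lung function: treatment, visit, their interaction and baseline.
- SAP 11.1.1.2, RCRM: treatment, baseline and treatment-by-day.
- SAP 11.1.3, mixed model for quality of life: treatment, visit, their interaction and baseline.

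**Display.** By default (SAP 8) placebo is combined over cohorts. The exception is SAP 10.1.6, where the OCS dose-time plots are shown separately for each dose cohort.

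**Status.** SAP 7.4.1 and 7.5 say there is no formal hypothesis testing, that tests are exploratory, and that multiplicity is not adjusted for.

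**The concern.** Randomisation makes active and placebo comparable within a cohort. It does not make cohorts comparable with each other, because patients reach a cohort by when they are available. In a single-dose contrast, 8 of the 12 placebo patients were randomised in other enrolment periods. Any change over time in patients, taper and rescue practice or visit conduct is then mixed with dose.

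Drift is plausible, though not shown. The Protocol synopsis gives a study duration of about two years. Protocol 6.3.1 allows COVID-19 flexibility in visits. Rescue rests partly on investigator judgement (Protocol 7.1.6.3). Steroid data come from an electronic diary for some patients and a paper-based log for others (SAP 10.1.1).

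At stake is how the secondary steroid-sparing results are read across doses. If steroid use fell from cohort to cohort for reasons unrelated to drug, 5 mg/kg would look steroid-sparing and 1 mg/kg would look harmful. For combined active v combined placebo the issue is mainly efficiency: differences between cohorts stay in the residual.

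**Working it through.** **Inputs.** 8 active + 4 placebo per cohort, three cohorts (Protocol 4.1, SAP 5.3). Total 3 × (8 + 4) = 36, with 24 active and 12 placebo, as Protocol section 5 states. There is no power calculation to reproduce (SAP 6).

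**Assumption.** Outcomes shift by -d, 0, +d in Cohorts 1, 2, 3; there is no drug effect; the baseline covariate does not carry the shift; residual SD is 1. The documents give no value, so d runs from 0 to 1 SD.

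**Per-dose bias.** Pooled placebo mean = [4(-d) + 4(0) + 4(d)]/12 = 0. Dose means are -d, 0, +d, so the contrasts are biased by -d, 0, +d. If d were 1 mg/day, they would be -1, 0 and +1 mg/day.

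**Combined contrast, bias.** Active mean = [8(-d) + 8(0) + 8(d)]/24 = 0 and placebo mean = 0, so the bias is 0.

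**Combined contrast, error term.** Treatment is taken as two levels, without the covariate (34 residual df). Drift adds (16d² + 8d²)/34 = 0.706d² to the expected error variance:

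- d = 0.5: 1 + 0.176 = 1.176, so the estimated SE is about √1.176 = 1.08 times the true SE.
- d = 1: 1.706, so about 1.31 times.

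The true SE is √(1/24 + 1/12) = 0.354 SD.

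**Simulated rejection rates** (200,000 trials per row, two-sided 0.05, no drug effect, baseline covariate omitted):

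| d (SD per step) | 1 or 5 mg/kg v pooled placebo | 5 v 1 mg/kg | Combined, no cohort | Combined, with cohort |
|---|---|---|---|---|
| 0 | 0.05 | 0.05 | 0.049 | 0.05 |
| 0.25 | 0.08 | 0.16 | 0.046 | 0.05 |
| 0.5 | 0.17 | 0.47 | 0.034 | 0.05 |
| 0.75 | 0.31 | 0.79 | 0.022 | 0.05 |
| 1.0 | 0.47 | 0.95 | 0.011 | 0.05 |

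The 5 v 1 mg/kg column is not a planned steroid-burden test. It shows how a dose-response reading would behave.

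**Taper endpoints.** With assumed success rates of 30%, 50% and 70% by cohort and no drug effect, the apparent per-dose differences are -20, 0 and +20 percentage points. Fisher rejection (exact enumeration) is 0.076 for the low and high doses, against 0.023 when the rate is 50% throughout.

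**If balance is lost.** Number the cohorts 0, 1, 2. Suppose the EE Set loses two placebo patients from Cohort 3. The placebo mean index becomes (4×0 + 4×1 + 2×2)/10 = 0.8, against 1.0 for active. Active minus placebo is then biased by 0.2d.

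**Price of cohort-adjusted dose contrasts.** Each dose is in effect compared with its own 4 placebo patients:

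- SE: √(1/8 + 1/4) = 0.612 v √(1/8 + 1/12) = 0.456 SD; ratio 1.34.
- 95% half-width: 1.25 v 0.93 SD.
- Power for a 1 SD effect: 35% v 57%.
- Bias is 0 and type I error about 0.05 at every d tested.

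**Price in the combined GLM.** Residual df with intercept, two-level treatment and baseline: 36 - 3 = 33. Cohort takes 2, leaving 31.

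**The case against.** **Pooling is a reasonable choice.** It makes use of scarce placebo patients, and concurrent-only contrasts cost 34% in SE. This stands, and is why the pooled per-dose contrasts should remain.

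**The design limits drift.** Every cohort follows the same taper to the same target, and the steroid model adjusts for baseline dose. Drift in starting dose is therefore largely absorbed. This stands for that source; changes in taper or rescue practice after baseline are not covered.

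**Everything is exploratory.** The primary endpoint is the incidence of adverse events and no dose-trend test is specified. This limits the weight of the point but does not remove it: SAP 10.1.3 presents confidence intervals and p-values, and SAP 3.2 foresees use in regulatory submissions.

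**Balance is protected.** Replacements take the original patient's assignment (SAP 5.3), and the mITT Set keeps every dosed patient. That is only partial protection. A dosed patient and a same-arm replacement both count in mITT, and the EE Set (SAP 7.1.3) drops patients with fewer than four doses or with major deviations.

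**Stronger readings that a reader might infer, and that the documents do not support:**

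- *Placebo is never shown by cohort.* SAP 10.1.6 presents OCS profiles, including individual ones, separately for each dose cohort. What is missing is a table or contrast.
- *The per-dose comparator is wholly non-concurrent.* Four of the 12 were randomised with the dose, and follow-up can overlap because a cohort may open once the previous one is fully randomised.
- *The combined contrast is biased as planned.* It is not, under 2:1 balance.
- *A placebo-by-cohort table would settle the matter.* With 4 per cohort, the SE of a Cohort 3 v Cohort 1 difference is √(1/4 + 1/4) = 0.71 SD. The 95% half-width is about 1.6 SD (9 df, all placebo patients) to 1.7 SD (6 df, those two cohorts only). The table makes large drift visible and cannot exclude moderate drift.

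**Conclusion.** The point holds as an analysis-choice issue. The specified efficacy analyses ignore the stratum within which patients are randomised, and the per-dose contrasts rest mainly on placebo patients from other cohorts. Their bias is -d, 0 and +d under linear drift not carried by baseline. At 0.5 SD per step, the low and high doses would each be declared different from placebo in about 17% of trials with no drug effect.

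The combined-active contrast is unbiased under 2:1 balance but conservative: 0.034 at 0.5 SD and 0.011 at 1 SD. It becomes biased only if exclusions or replacements unbalance the cohorts.

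These figures rest on assumed linear drift, equal residual variance and no help from the covariate. A reader might infer that drift occurred, or that any dose gradient would be false; the documents support neither. The consequence is for reading the secondary and exploratory efficacy results, not for a confirmatory error rate or the primary safety endpoint.

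**What to change.** **Combined active v combined placebo**

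- Add cohort as a class term to the OCS AUC GLM, the lung-function MMRM and the quality-of-life mixed model.
- In the RCRM add cohort and cohort-by-day. The contrast there is a slope, and a cohort main effect adjusts level only.
- Stratify the combined log-rank and Wilcoxon tests by cohort.

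**Each dose v placebo**

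- Keep the pooled-placebo contrasts as planned, and state beside them that 8 of the 12 placebo patients come from other cohorts.
- Tabulate placebo by cohort, next to pooled placebo, for the OCS endpoints and key lung-function endpoints.
- Report cohort-adjusted per-dose contrasts as a sensitivity analysis only, given the 1.34-fold SE.

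**Cost.** Two of about 33 residual degrees of freedom in the combined GLM, and some extra tables. No new data are needed. Adding cohort to the combined models does not remove the per-dose bias; the statement, the table and the sensitivity analysis are there to expose it.

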10.1.4. Study Drug Adjusted OCS Burden

Since a missed dose in study treatment is likely to affect OCS dose, in order to isolate the effect of treatment, the above mentioned OCS dose, change from baseline and percent change from baseline analyses will be repeated, but excluding a window around a missed dose of study treatment, where a window is defined as 30 days after the previous dose and restart on the day of the next administered dose. Active treatment and placebo will be compared in the same way as in time adjusted OCS burden in the previous section.

10.1.5. Achievement of Target Taper Dose of Prednisone 5 mg/day (or Equivalent) and Maintained Through Week 24

The number and percentage of patients who have achieved the following will be summarized.

1. **Ability to Taper:** Taper OCS dose level down to 5mg/day or less at any time and remained for at least 5 consecutive days.
2. **Maintain Taper:**
 - a. Taper OCS dose level down to 5mg/day or less at any time and remained for at least 30 consecutive days.
 - b. Taper OCS dose level down to 5mg/day or less at any time and remained for at least 60 consecutive days.
 - c. Taper OCS dose level down to 5mg/day or less at any time and remained for at least 90 consecutive days.
 - d. Taper OCS dose level down to 5mg/day or less at any time and remained for at least 115 consecutive days

- e. Time to first relapse of taper for sarcoidosis. Defined as the duration from the first day of hitting 5mg (plus 5 consecutive days) to when >5mg is needed. If the reason for increase in OCS is unrelated to sarcoidosis (as identified from the eCRF) then that episode will not count as a relapse and counting of the duration will recommence on the next day on which 5mg is achieved. For patients who maintain 5mg after successful taper will be censored at 30 days after last dose or EOS (if earlier). Patients who never reach 5 mg will be assigned a duration of 1 day and be classified as a censored data point.
- f. Proportion of days at 5mg or less ignoring diary days when OCS dose was increased >5mg for non-sarcoidosis events (i.e. same exclusion as the Time to First Relapse endpoint)
- g. Proportion of days at 5mg or less including all diary days (i.e. even those when OCS dose was increased >5mg for non-sarcoidosis events)

In each of the above endpoints, when study drug dosing is missed, OCS diary data >30 days after previous study drug infusion will be ignored until dosing restarted as described in Section 10.1.4.

For each of the first 4 taper maintenance endpoints above, 2-sided Fisher's exact test will be performed between each individual active treatment arm and combined placebo, using the pseudo code below.

```
proc freq data = taper (where=(treatment in ("Treatment A", "Placebo")));
  table taper_var*treatment / fisher;
run;
```

For the 5th of the "Maintain taper" endpoints (i.e. Time to first relapse of taper), Kaplan-Meier methods will be used to derive estimates of median (& 95% CI) of the time to first taper relapse. A log-rank test will be performed between each individual/combined active treatment arm and placebo to obtain p-values versus placebo. Kaplan-Meier curve will be presented as well. The following pseudo SAS code is used.

```
proc lifetest;
  time duration*status(0);
  strata treatment / test=logrank;
run;
```

where 0 indicates no relapse.

For 6th and 7th of the "Maintain taper" endpoints (i.e. Proportion of days at 5mg or less) descriptive statistics (Mean, SD etc) will be used to informally compare groups. A Wilcoxon rank sum test will be performed between each individual/combined active treatment arm and placebo to obtain p-values versus placebo. The following pseudo SAS code will be used.

aTyr Pharma, Inc.
Study ATYR1923-C-002 Statistical Analysis Plan
IND#: 133692

FINAL Version 1.0
2021-08-02

```
proc nparlway wilcoxon correct=no;  
  class treatment;  
  var days_at_5mg;  
  exact wilcoxon;  
run;
```

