6. SAMPLE SIZE

For this study, no prospective calculations of statistical power have been made. The sample size has been selected to provide information on safety, tolerability, immunogenicity, PK and efficacy following single doses of ATYR1923. Any p-values to be calculated will be interpreted in the perspective of the explorative character of this study.

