7.4. Planned Study Analyses

7.4.1. Statistical Summaries: Descriptive and Inferential

There will be no formal hypothesis testing for this study. All p-values shown from exploratory analyses will be rounded to and displayed in four decimals. If a p-value less than 0.0001 occurs it will be shown in tables as <0.0001.

Descriptive summaries of variables will be provided where appropriate. For continuous variables, the number of non-missing values (n), mean, standard deviation, median, minimum, and maximum will be tabulated by treatment. For categorical variables, the counts and proportions of each value will be tabulated by treatment. Expansion of descriptive table categories within each treatment may occur if such elaborations are thought to be useful.

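### SAP 10.1.4 removes the doses recorded in a missed-infusion window but, under the 10.1.3 formula, keeps the window's time, refilled with the average of the two edge doses

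*SAP*

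**What the plan says.** SAP 10.1.3 defines each patient's time-adjusted AUC as the sum of (C_t + C_t')(t' − t) divided by 2(N − M). The result "approximates the mean steroid usage post-baseline for each patient". Two definitions matter here. The upper end of each trapezoid, t', "is the study day of the next known OCS daily dose after day" t. And "M and N are start and end study days of the analysis periods of interest": Day 1 or Day 51 up to 30 days after the last infusion, or to the last known steroid dose if that comes first.

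SAP 10.1.4 then repeats the dose, change and percent-change analyses, "but excluding a window around a missed dose of study treatment, where a window is defined as 30 days after the previous dose", with data resuming on the day of the next infusion given. The stated reason is that a missed infusion probably affects steroid use, so removing that stretch should leave a cleaner estimate of the drug's effect. The section contains no formula and does not say how N − M changes.

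SAP 7.3.3.4 adds that steroid dose levels are not imputed.

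**The concern.** Once the window's diary days are set aside, the last day before the window has the restart day as its next known dose. The formula joins those two days with a single trapezoid, and N − M still counts every day between them. The recorded doses are gone, but the window's time remains, valued at the average of its two edges.

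The restart-day dose may itself have been raised because of the missed infusion. It would then set half of the value assigned to the whole window. An analysis meant to remove the influence of a missed infusion could keep much of it, or all of it.

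**Working it through.** **Inputs from the documents.** Infusions are every 4 weeks (Days 1, 29, 57, 85, 113, 141). The end-of-study visit is Day 169, and each cohort plans 8 active patients. Two consecutive missed doses end treatment (protocol 6.4.1), so a gap followed by a restart is one missed dose.

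**Assumptions.** The Day 85 infusion is missed. Dosing restarts on Day 113. The last known steroid dose is on Day 169. The background dose is 5 mg/day from Day 51, plus the rescue shown. The documents give no such profiles; these are illustrations.

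**Window.** It starts at 57 + 30 = Day 87 and ends on Day 113, so it lasts 26 days. With Days 51 to 169, N − M = 118 and 26/118 = 22.0%. With Days 51 to 171 (141 + 30), 26/120 = 21.7%. With Days 1 to 171, 26/170 = 15.3%.

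**Check of the formula.** The plan states no AUC value to reproduce. With complete diary data at a constant 5 mg, the formula returns 5.00, as it should.

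**Comparison.** Days 88 to 112 are removed; Days 87 and 113 are the edges. A1 is the AUC over Days 51–87 and A2 the AUC over Days 113–169.

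- Literal: (A1 + 26 × edge average + A2)/118
- True exclusion: (A1 + A2)/(118 − 26) = (A1 + A2)/92

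| Assumed rescue | A1 | Bridge | A2 | Unadjusted | Literal | True exclusion | Literal − true |
|---|---|---|---|---|---|---|---|
| (a) 20 mg, Days 95–118 | 180 | 26 × 12.5 = 325 | 362.5 | 950/118 = 8.05 | 867.5/118 = 7.35 | 542.5/92 = 5.90 | 1.45 |
| (b) 20 mg, Days 109–130 | 180 | 325 | 542.5 | 920/118 = 7.80 | 1047.5/118 = 8.88 | 722.5/92 = 7.85 | 1.02 |
| (c) 20 mg, Days 80–126 | 292.5 | 26 × 20 = 520 | 482.5 | 1295/118 = 10.97 | 1295/118 = 10.97 | 775/92 = 8.42 | 2.55 |
| (d) 10 mg, Days 95–126 | 180 | 26 × 7.5 = 195 | 347.5 | 750/118 = 6.36 | 722.5/118 = 6.12 | 527.5/92 = 5.73 | 0.39 |
| (e) 20 mg, Days 95–112 | 180 | 26 × 5 = 130 | 280 | 860/118 = 7.29 | 590/118 = 5.00 | 460/92 = 5.00 | 0 |
| (f) none | 180 | 130 | 280 | 5.00 | 5.00 | 5.00 | 0 |

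In (a) the literal calculation removes 8.05 − 7.35 = 0.70 of the 8.05 − 5.90 = 2.15 that true exclusion removes, about one third. In (c) it removes nothing.

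**General form.** Literal − true = (26/118) × (edge average − mean over retained days). For (a): 0.220 × (12.5 − 5.90) = 1.45. The error is zero when the edge average equals the retained mean, and its sign can reverse. Over Days 1 to 171, with an assumed 15 mg to Day 14, 10 mg to Day 28, 5 mg after and no rescue, the literal value is 6.21 against 6.42, an error of −0.22.

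**Sensitivity.** Ending the period on Day 171 gives 7.31 vs 5.88, 8.81 vs 7.79 and 10.88 vs 8.35 for (a) to (c). Excluding Day 87 as well gives 7.42 vs 5.91 for (a) and 8.94 vs 7.89 for (b).

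**Effect on an arm mean.** Per affected patient in an arm of 8: 1.02/8 = 0.13, 1.45/8 = 0.18, 2.55/8 = 0.32 mg/day. In the planned combined active group of 24, the range is 1.02/24 = 0.04 to 2.55/24 = 0.11.

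**The case against.** The strongest reply is that 10.1.4 states the intention to exclude and speaks of restarting at the next infusion. That fits a calculation by segment, and a careful programmer might do it that way. This stands as a statement of intent, but nothing in the SAP tells the programmer to do so, and the only formula given does something else. One could also argue that excluded doses are still known, so the formula would not bridge the gap. On that reading the window's doses would be used after all, which defeats the section. The other shortcut, dropping the window's terms while leaving N − M unchanged, is also wrong: over Days 51 to 171 a constant 5 mg becomes 5 × 94/120 = 3.92.

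Two stronger readings are tempting, and the documents do not support them. A reader might infer that the window is not excluded at all. Its recorded doses are dropped, and row (e) shows a rescue wholly inside the window removed in full. A reader might also infer from row (b), where the adjusted 8.88 exceeds the unadjusted 7.80, that the adjustment goes in the wrong direction. True exclusion also rises there, to 7.85, so the fault is in the size of the move.

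The objection on importance largely stands. The endpoint list in SAP 4.2.2 does not name this version; it is a supplementary repeat. SAP 6 states "For this study, no prospective calculations of statistical power have been made", and SAP 7.4.1 states "There will be no formal hypothesis testing for this study". The individual dose-time plots in 10.1.6 would also make affected patients visible.

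**Conclusion.** The defect is real as the text is written: the 10.1.3 formula, applied to 10.1.4, keeps about 22% of the Day 51 period that the section sets out to remove. In the illustrations with a raised edge dose, the adjusted value is too high by 0.39 mg/day (10 mg rescue) to 2.55 mg/day (20 mg rescue across both edges). The bridging also sits badly with the rule against imputing steroid doses.

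The size rests on assumed profiles and applies only to patients who miss an infusion and restart. The documents foresee such patients, since 5 of 6 doses count as completion (protocol 6.5) and protocol 6.3.1 anticipates missed visits, but they give no number and no split by arm. A bias for or against active treatment therefore cannot be inferred. The main 10.1.3 analysis is unaffected. So are the 10.1.5 endpoints, which borrow the window but not the AUC formula. Moderate priority: correct it, but no primary conclusion depends on it.

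**What to change.** Give 10.1.4 its own formula. Compute trapezoids separately within each retained segment and never across an excluded window. Divide the sum of the segment AUCs by the sum of the segment lengths. State whether the 30th day after the previous infusion and the restart day count as retained. Apply the same rule to change and percent change from baseline, and to both analysis periods.

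The cost is one formula in the SAP and a small program change, with no new data. It is best made before treatment codes are opened.
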